5.2.1.2 Additional analysis

Besides sensitivity analyses, no additional analyses are planned.

5.2.1.3 Summary Measures

See 5.1.1

5.2.1.4 Assumption Checks and Alternative Analyses

A logistic regression includes the following assumptions:

- Binary dependent variable: This assumption is fulfilled trough the study design. (OMERACT/OARSI responder criteria, calculated into a binary yes or no score).
- Independence: This assumption is fulfilled through the study design.
- No severe multicollinearity: This assumption is fulfilled through the study design.
- Sufficient number of observations: The sample size was calculated based on approximately 20% responders in the control group and 40% responders in the intervention group, which would provide sufficient number of patients per group.

5.2.1.5 Missing Data

We are expecting the amount of missing data to increase with time, but we cannot retrace the individual reasons for missingness. The primary analysis will utilize multiple imputation, including variables such as gender, age, pain, function and disease activity at baseline and 3 months.

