2.3 Sample size

The sample size is calculated based on the primary outcome (proportion of OMERACT-OARSI responders) measured at 3 months. An OMERACT-OARSI responder rate between 26-46% is previously shown in hand exercise groups compared to 6-24% in usual care groups [13,14]. The between-group difference in primary outcome is estimated to 20% [15]. To account for multiple testing (primary and key secondary hypotheses), we will use a significance level of 1%, and 90% power. With a between-group difference of 20% and a usual care responder rate of 20%, we need to include 150 patients in each group. To account for a possible drop-out rate of 25% due to the digital nature of the study, a total of 376 patients are needed.

More detailed information is available in the study protocol [12].

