2.4 Statistical Framework

2.4.1 Hypothesis Test

This trial is designed to assess if using the Happy Hands app in addition to usual care is superior to usual care alone with regards to probability of OMERACT/OARSI response at 3 months.

 The primary null hypothesis posits that there is no difference in probability of OMERACT/OARSI response between Happy Hands in addition to usual care compared to usual care alone at 3 months.

> Statistical Analysis Plan Happy Hands Diakonhjemmet Hospital

Page 8 of 27

• The primary alternative hypothesis is that using the Happy Hands app in addition to usual care is superior to usual care alone with regards to probability of OMERACT/OARSI response at 3 months.

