5.2 Analysis Methods

5.2.1 Primary Outcome

5.2.1.1 Primary Analysis

For analysis of the primary outcome a logistic regression with group as independent variable and OMERACT/OARSI response (yes/no) at 3 months as dependent variable will be conducted. The analysis will adjust for study center, the stratification factor used in the randomization. Probability of being a responder as well as risk difference will be calculated using the adjusted risk and risk difference estimators [25].

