5.2.2 Secondary Outcomes

5.2.2.1 Secondary Analyses

a) OMERACT/OARSI responders at 6 months
For the secondary outcome of probability of OMERACT/OARSI response in the two groups at 6 months, we will conduct the same analysis as for the primary outcome.

Secondary continuous outcomes will be analysed using linear regression. The analyses will, in addition to randomization group, adjust for baseline level of the outcome and study center. Missing values will be handled using multiple imputation.

b) Health economic evaluation

Aim: To assess whether the Happy Hands app in combination with usual care is a cost-effective treatment strategy for patients with hand OA compared to usual care alone.

Statistical software: Mainly STATA. Excel for bootstrap, plotting results on the cost-effectiveness plane and for construction the cost-effectiveness acceptability curve.

Perspective on costs: health care perspective as primary analysis, inclusion of production loss in explorative analysis.

Cost of the intervention: The Happy Hands app is not yet commercially available, hence has no official list price or yearly fee. Based on the cost of development and maintenance and the size of the eligible patient population, we assume that the app will be offered at an annual subscription fee of NOK 150 (EUR 13).

Identification of resources: patient self-reported in questionnaire, asked about resource use items as displayed in Table 1.

Measurement of resource use: patient self-reported in questionnaire. May add information from clinical expertise if needed, e.g. patient reports a rehabilitation stay, but not duration.

Statistical Analysis Plan Happy Hands Diakonhjemmet Hospital

Page 22 of 27

Valuation of resource use data: As far as possible, we will use unit prices reported in the Directorate of Medical Products database for use in health technology assessments (https://view.officeapps.live.com/op/view.aspx?src=https%3A%2F%2Fwww.dmp.no%2Fglobalassets %2Fdocuments%2Foffentlig-finansiering-og-pris%2Fdokumentasjon-tilmetodevurdering%2Fenhetskostnader-v1.5.xlsx&wdOrigin=BROWSELINK), this includes the price per in-patient day at hospital.

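### The variables named for imputing the primary outcome include neither randomised group nor study center; if only those are used, the risk difference shrinks by about the share of patients missing.

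*SAP*

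**What the plan says.** The primary analysis (SAP 5.2.1.1) is "a logistic regression with group as independent variable and OMERACT/OARSI response (yes/no) at 3 months as dependent variable". On covariates it adds: "The analysis will adjust for study center, the stratification factor used in the randomization". The model therefore has two terms, group and center.

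SAP 5.2.1.5 is the only description of how missing primary outcome data are imputed: "The primary analysis will utilize multiple imputation, including variables such as gender, age, pain, function and disease activity at baseline and 3 months". The variables are given as examples, so the list is open. Group and center are not among them, and nothing says that imputation is done separately by arm. The other mentions of multiple imputation (5.2.2.1, including its health economic part, and 5.2.2.4) do not name group or center either.

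On the amount of missing data, 2.3 enlarges the sample "To account for a possible drop-out rate of 25% due to the digital nature of the study".

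For response at 6 months, 5.2.2.1 a) says "we will conduct the same analysis as for the primary outcome". SAP 5.2.2.4, however, reserves multiple imputation for the cost-effectiveness data and puts the other secondary analyses on complete cases.

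**The concern.** An imputation model should contain every variable of the analysis model, above all the one whose effect is being estimated. Here the named list holds neither.

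The 3-month pain, function and disease activity scores do not fill the gap. They are the components of the response (5.1.2), so a patient who does not return the 3-month form lacks all three. What remains from the list is age, gender and the baseline scores, which randomisation balances between arms. Without group, an app patient and a control patient with the same baseline get the same imputed chance of response. That amounts to assuming no treatment effect among drop-outs, and the plan states no such assumption.

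At stake are the primary risk difference, its test at the 1% level, and the confidence limit that 2.4.4 compares with 20%. Nothing else in the plan is certain to reveal the problem: 5.2.1.6 offers missing-data sensitivity analyses only if judged necessary.

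**Working it through.** **Inputs from the SAP.** Control response 20%, app 40%, 150 per group, alpha 0.01, power 90%, loss 25%, total 376 or 188 per arm (2.3); 1:1 allocation and 20 sites (2.2).

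**Assumptions, not in the SAP.** Two-sided test (2.4.1 gives the null as "there is no difference in probability of OMERACT/OARSI response" without naming the sidedness). Drop-outs lack all 3-month data. Loss is completely at random and, unless stated, equal by arm.

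**1. The plan's own figure.** The plan says: "With a between-group difference of 20% and a usual care responder rate of 20%, we need to include 150 patients in each group". With unpooled variance, n = (2.576 + 1.282)² × (0.2×0.8 + 0.4×0.6) / 0.20² = 149 per group. The pooled formula gives 154. One-sided versions give 131 and 135. The stated 150 is thus reproduced two-sided, which supports that assumption.

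**2. Expected shrinkage.** Let d be the share missing in each arm and p̄ the response rate pooled over the observed patients. Without group in the model:
- app: (1−d)×40% + d×p̄
- control: (1−d)×20% + d×p̄
- difference: (1−d)×(40% − 20%)

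At d = 0.25 and p̄ = 30%:
- app: 0.75×40 + 0.25×30 = 37.5%
- control: 0.75×20 + 0.25×30 = 22.5%
- difference: 15 points, not 20

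At other values of d:

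| Loss in each arm | Expected difference |
|---|---|
| 10% | 18 points |
| 20% | 16 points |
| 25% | 15 points |
| 30% | 14 points |

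Unequal loss gives a similar answer. With 15% lost in control and 35% in the app arm, p̄ = (0.85×20 + 0.65×40)/1.50 = 28.7%. Control becomes 21.3%, app 36.0%, and the difference 14.7 points. Reversing the two loss rates also gives 14.7.

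**3. Simulation.** Settings: 188 per arm, 25% loss, 20 imputations, Rubin's rules, unadjusted risk difference, two-sided 0.01, 1,000 trials per row. Response is imputed by logistic regression on one baseline covariate, with or without group.

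| Latent correlation of baseline with outcome | Without group: estimate, power | With group: estimate, power |
|---|---|---|
| 0 | 14.9 points, 63.5% | 20.0 points, 85.5% |
| 0.3 | 15.0 points, 65.3% | 20.0 points, 88.0% |
| 0.5 | 15.0 points, 64.1% | 20.2 points, 89.4% |

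A better baseline predictor does not remove the shrinkage. A second simulation (2,000 trials, imputing at the pooled rate or by arm) gave 14.9 points and 62% power without group, against 19.9 points and 87% by arm. As a check, analysing complete cases only, 188×0.75 = 141 per arm, has power 86.8% by formula, so imputation without group does worse than not imputing.

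**Limits.** The simulations omit center and impute the yes/no response directly rather than its components.

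**The case against.** The strongest reply is that the list is only illustrative. Age and gender are not in the primary model, so the list may be meant as auxiliaries to be added to group and center, which 5.2.1.1 already specifies. No section excludes group from the imputation or says that the arms are pooled. This stands: a reader might infer that the plan prescribes a biased primary analysis, and the text does not support that. The bias follows only if group is not added. It does not clear the plan, because the choice moves the estimate from about 20 to 15 points in an open-label trial (2.1) and should be written down in advance. If a conservative assumption about drop-outs were intended, it would have to be stated.

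Three further objections also stand.
- **Center.** A reader might blame both omissions for the shrinkage. Randomisation is stratified by site (2.2), so leaving out center does not itself pull the effect towards zero.
- **Six months.** A reader might infer that the 6-month response is biased in the same way. Under 5.2.2.4 it would not be imputed at all. If it were imputed, patients with observed 3-month components would carry treatment information, so the 3-month figures do not transfer.
- **Size.** Where the 3-month form is partly answered, the observed components carry group information and the shrinkage is smaller. The 25% is a planning allowance, not a forecast.

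**Conclusion.** The point holds as a conditional one. SAP 5.2.1.5 does not fix the two variables of its own analysis model, and following the named variables alone biases the primary estimate towards zero. Under the plan's 20% v 40% and 25% loss, the risk difference falls from 20 to about 15 points and power from about 86-89% to about 62-65%. These figures rest on complete 3-month non-response, equal loss completely at random, and a two-sided test. All of the shrinkage is due to group. The omission of center is a matter of consistency. No conclusion on the 6-month response is possible until the plan says whether it is imputed.

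**What to change.** Replace the imputation sentence in 5.2.1.5 with text to this effect:

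> Missing 3-month pain, MAP-Hand and disease activity scores will be multiply imputed with randomised group in the model (or separately by group), study center, age, gender, the baseline values of the three scores, and their 6-month values as auxiliaries. Response will be derived after imputation.

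The 6-month values are already collected and help for patients who missed the 3-month form but returned the later one. Including them is an improvement; including group is the essential change.

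For the 6-month response, first reconcile 5.2.2.1 with 5.2.2.4. The same conflict affects the continuous secondary outcomes, which 5.2.2.1 imputes and 5.2.2.4 analyses as complete cases. If the 6-month response is to be imputed, include group there too, with the 3-month components as predictors.

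The cost is SAP wording and a few lines of code, with no new data. With 20 sites and 188 per arm there are on average 188/20 = 9.4 patients per site and arm before loss, so small sites may need pooling or a random effect in the imputation. This is most pressing if imputation is run separately by group; a single model with a group term is the less demanding option.

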5.2.1.6 Sensitivity Analyses

Statistical Analysis Plan Happy Hands Diakonhjemmet Hospital

Page 21 of 27

Kommentert [[name]]: Skal center justeres for? Vanlig å justere for stratifiseringsvariabler brukt i randomiseringen.

For the primary endpoint, a sensitivity analysis will be carried out adjusting for recruitment site (, baseline pain, disease activity and function (which are the measures included in the OMERACT/OARSI responder criteria). Additional sensitivity analyses may be conducted, adjusting for variety in usual care (participating in osteoarthritis courses).

If deemed necessary, sensitivity analyses will also be conducted to address missing data and subgroup data.

5.2.1.7 Subgroup Analyses

No subgroup analyses are planned outside of the sensitivity analyses.

5.2.2 Secondary Outcomes

5.2.2.1 Secondary Analyses

a) OMERACT/OARSI responders at 6 months
For the secondary outcome of probability of OMERACT/OARSI response in the two groups at 6 months, we will conduct the same analysis as for the primary outcome.

Secondary continuous outcomes will be analysed using linear regression. The analyses will, in addition to randomization group, adjust for baseline level of the outcome and study center. Missing values will be handled using multiple imputation.

b) Health economic evaluation

Aim: To assess whether the Happy Hands app in combination with usual care is a cost-effective treatment strategy for patients with hand OA compared to usual care alone.

Statistical software: Mainly STATA. Excel for bootstrap, plotting results on the cost-effectiveness plane and for construction the cost-effectiveness acceptability curve.

Perspective on costs: health care perspective as primary analysis, inclusion of production loss in explorative analysis.

Cost of the intervention: The Happy Hands app is not yet commercially available, hence has no official list price or yearly fee. Based on the cost of development and maintenance and the size of the eligible patient population, we assume that the app will be offered at an annual subscription fee of NOK 150 (EUR 13).

Identification of resources: patient self-reported in questionnaire, asked about resource use items as displayed in Table 1.

Measurement of resource use: patient self-reported in questionnaire. May add information from clinical expertise if needed, e.g. patient reports a rehabilitation stay, but not duration.

Statistical Analysis Plan Happy Hands Diakonhjemmet Hospital

Page 22 of 27

Valuation of resource use data: As far as possible, we will use unit prices reported in the Directorate of Medical Products database for use in health technology assessments (https://view.officeapps.live.com/op/view.aspx?src=https%3A%2F%2Fwww.dmp.no%2Fglobalassets %2Fdocuments%2Foffentlig-finansiering-og-pris%2Fdokumentasjon-tilmetodevurdering%2Fenhetskostnader-v1.5.xlsx&wdOrigin=BROWSELINK), this includes the price per in-patient day at hospital.

If some unit price is not available in this database, we will use publicly available reimbursement rates. For visits to an occupational therapist in primary care, we will assume an average duration of visit and wage of therapist. Medical and technical equipment, such as a bread knife or vegetable knife with built-up handles, key for opening jars, or self-opening scissors, will be based on market prices (e.g. https://www.velferdsbutikken.no/categories/hjelpemidler-kjokken).

Identification of outcomes: self-reported in questionnaires.

Measurement of outcomes: Health related quality of life measured by the EQ-5D-5L. In the analysis of EQ-5D-5L, we will adjust for baseline imbalances using the method recommended by Manca and co-workers [26], if warranted.

Valuation of outcomes: Primary analysis based on the Norwegian EQ-5D-5L tariff by Garratt and cocorkers [27], sensitivity analysis with the UK Devlin tariff [28].

Analysis population: primary analysis with ITT population, may explore PP as sensitivity analysis.

Timing: Health-related quality of life is measured at baseline, 3 and 6 months, while costs are measured at 3 and 6 months.

Discounting: not relevant due to trial duration

Cost-effectiveness threshold: threshold suggested for Norway at time of analysis, currently NOK, 275,000 per QALY for patients with osteoarthritis

Statistical decision rule: Cost-effective if incremental cost-effectiveness ratio below threshold and if intervention has a higher probability of being cost-effective than comparator based on bootstrap results.

Analysis of resource use: mean cost per patient reported in 2024 EUR, will use valuta converter provided by "Norges Bank" to convert NOK to EUR using the average exchange rate in 2024 (https://www.norges-bank.no/tema/Statistikk/valutakurser/?tab=currency&frequencyTab=3).

Analysis of outcomes: mean QALY per patient. We expect no effect on mortality, hence any QALY gain will be a result of improvements in function and well-being. QALYs will be calculated based on the area under the curve approach. We will assume that transition between different health utility values will take place halfway between two measurements.

Missing data: if whole questionnaire of EQ-5D-5L is missing, multiple imputation, if single questions are missing, simple imputation. Costs are assumed to be missing only if the whole questionnaire is missing, if the questionnaire is missing, we will impute using multiple imputation.

Statistical Analysis Plan Happy Hands Diakonhjemmet Hospital

Page 23 of 27

Analysis of cost-effectiveness: ICER=difference in mean costs/difference in mean QALY

Sampling uncertainty: We will use non-parametric bootstrapping to assess the degree of uncertainty around the ICER. We bootstrap costs and QALY 10,000 times with replacement, recalculate ICERS and plot the results on the cost-effectiveness plane. The likelihood of cost-effectiveness will then be calculated as the proportion of all bootstrapped samples below the cost-effectiveness threshold value. A cost-effectiveness acceptability curve will be constructed to illustrate how sensitive the conclusion is to varying levels of threshold values. This approach is one of several alternatives recommended for trial-based cost-effectiveness analyses [16].

Subgroup analysis: Per protocol population

Sensitivity analysis: Devlin tariff for the EQ-5D-5L

Explorative analysis: including loss of production

c) Effect on secondary outcomes (pain, hand function, grip strength, disease activity and guality of care)

To assess the effect of using the Happy Hands app in addition to usual care compared to usual care only on secondary outcomes of pain, hand function, grip strength, disease activity and quality of care, we will use multiple linear regression with the mean change scores at 3 and 6 months as dependent variables and group as independent variable, adjusting for baseline values for the variable of interest and recruitment sites.

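### Adjustment of QALYs for baseline utility is conditional without a criterion, and the plan does not say that the adjusted difference feeds the ICER and each bootstrap sample

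*SAP*

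**What the plan says.** Cost-effectiveness at 6 months is key secondary hypothesis b) in SAP section 2.4.2. Section 5.2.2.1 b) sets out its analysis:

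- **Baseline adjustment.** "In the analysis of EQ-5D-5L, we will adjust for baseline imbalances using the method recommended by" the authors of reference 26. The sentence closes with a condition: "and co-workers [26], if warranted". No size of imbalance, test, time point or decision-maker is given there or elsewhere. Section 4.3 says only that clinically important imbalances will be noted.
- **QALY.** Area under the curve from EQ-5D-5L at 0, 3 and 6 months: "We will assume that transition between different health utility values will take place halfway between two measurements".
- **ICER.** "ICER=difference in mean costs/difference in mean QALY".
- **Bootstrap.** "We bootstrap costs and QALY 10,000 times with replacement, recalculate ICERS and plot the results on the cost-effectiveness plane".
- **Decision rule.** "Cost-effective if incremental cost-effectiveness ratio below threshold and if intervention has a higher probability of being cost-effective than comparator based on bootstrap results". The threshold is currently NOK 275,000 per QALY.

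By contrast, the rule for continuous secondary outcomes in the same section has no condition: "The analyses will, in addition to randomization group, adjust for baseline level of the outcome and study center". Part c) repeats this for pain, hand function, grip strength, disease activity and quality of care.

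**The concern.** Baseline utility is a component of the QALY as defined here, so a chance difference between arms at baseline passes straight into the unadjusted QALY difference. It passes in a second time through its correlation with the 3- and 6-month utilities. Adjustment removes this noise with a variable that is already collected. The plan names a method for it and then leaves its use to an unstated judgement.

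The same data can therefore yield two ICERs, and the plan does not say in advance which one decides. Even if adjustment is used, the text leaves open whether the bootstrap repeats it. If it did not, the two limbs of the decision rule would rest on different QALY differences. Both analyses agree when net benefit is large or the imbalance is small; in between they can differ.

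**Working it through.** The SAP states no precision figure for the economic analysis, so there is none to reproduce.

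**From the SAP:** visits at 0, 3 and 6 months with halfway transition; threshold NOK 275,000; app fee NOK 150 per year; 376 patients, so 376/2 = 188 per arm (section 2.3).

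**Assumed:** equal utility SD at each visit, 0.15 to 0.20; common correlation r between visits, 0.4 to 0.8; cost SD NOK 5,000 to 15,000, independent of QALY; incremental cost NOK 150; true utility gain 0.02 at both follow-ups.

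**1. QALY weights.** Halfway transition gives 1.5, 3 and 1.5 months, so QALY = 0.125·u0 + 0.25·u3 + 0.125·u6. Baseline has direct weight 0.125 of 0.5 year, or 25%.

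**2. Noise in the QALY difference.** In units of the utility variance:
- cov(QALY, u0) = 0.125 + 0.375r
- var(QALY) = 0.09375 + 0.15625r
- r = 0.4: R² = 0.275²/0.15625 = 0.484; SE ratio 1/√(1 − R²) = 1.39
- r = 0.6: R² = 0.35²/0.1875 = 0.653; ratio 1.70
- r = 0.8: R² = 0.425²/0.21875 = 0.826; ratio 2.40

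**3. Size of a chance imbalance.** The SE of the baseline difference is SD·√(2/188): 0.0155 for SD 0.15 and 0.0206 for SD 0.20. A difference of 0.02 is thus about one SE. It moves the unadjusted QALY difference by 0.02·(0.125 + 0.375r) = 0.0055 to 0.0085, worth NOK 1,513 to 2,338 at the threshold.

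**4. Noise in net benefit.** The decision also involves cost, which adjustment does not sharpen. The per-patient variance of net benefit is 275,000²·var(QALY) + (cost SD)², with the residual QALY variance used when adjusted.
- Least favourable corner (r = 0.4, SD 0.15, cost SD 15,000): unadjusted √(265.9 million + 225 million) = 22,156; adjusted √(137.2 million + 225 million) = 19,031; ratio 1.16.
- Most favourable corner (r = 0.8, SD 0.20, cost SD 5,000): unadjusted √(661.7 million + 25 million) = 26,205; adjusted √(115.3 million + 25 million) = 11,846; ratio 2.21.

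**5. Verdicts.** True QALY gain = 0.375 × 0.02 = 0.0075; true net benefit = 275,000 × 0.0075 − 150 = NOK 1,912.5. The verdict is taken as the sign of estimated net benefit. Under a conditional rule, disagreement with always adjusting can arise only when the imbalance stays below the trigger. Approximate shares of trials in which the verdict differs from always adjusting:

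| Adjustment triggered when | Gain 0.02 | Gain 0.04 |
|---|---|---|
| Never | 11%–23% | 1%–9% |
| Baseline difference > 0.01 | 2%–4% | 0–0.6% |
| Baseline difference > 0.02 | 6%–10% | 0.2%–2% |
| Baseline difference has p < 0.05 | 10%–21% | 0.7%–7% |

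For gain 0.02, the verdict is wrong in 14%–27% of trials with no adjustment and in 2%–20% with adjustment always.

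**The case against.** The strongest reply is that the plan does not propose to leave QALYs unadjusted. It names a method, and the two analyses differ most when the imbalance is large, which is when the condition would most likely be met. This stands as to size: 11% to 23% is an upper bound, reached only if adjustment is never triggered. It does not remove the point, because the table shows that the size depends on the trigger the plan leaves unstated.

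Second, reference 26 concerns controlling for baseline utility when estimating mean QALYs, so the named method can reasonably be read as supplying the QALY difference in the ICER and in every recalculation. A reader might infer that the ICER and bootstrap text contradicts the adjustment sentence. It does not; the step is unstated.

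Third, a reader might infer a choice driven by outcomes, or bias. The documents support neither. They do not say who decides or when, a decision taken on baseline data alone would not depend on outcomes, and under randomisation a chance imbalance is noise.

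Fourth, it is tempting to set the NOK 1,513 to 2,338 shift against the NOK 150 app fee. That comparison does not bear on the decision, because the ICER numerator is the difference in all healthcare costs. Using NOK 150 as the incremental cost above assumes that every other cost is equal between arms.

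Finally, the unconditional rule for continuous outcomes might be said to cover this already. It adjusts for the baseline level of the outcome, which a QALY does not have; part c) does not list EQ-5D-5L; and the economic section sets its own conditional rule.

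**Conclusion.** The point holds as a gap in specification with a better method available at almost no cost. The wording gap itself is certain: the adjustment is conditional, no criterion exists, and its place in the ICER and bootstrap is not stated.

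The size is much less certain, since every utility and cost input is assumed. On those ranges, not adjusting inflates the standard error by a factor of 1.4 to 2.4 for the QALY difference and, more relevant to the decision, 1.2 to 2.2 for net benefit. The top of each range needs a correlation of 0.8 between all visits. The share of trials in which the verdict would differ from always adjusting runs from about 2% to an upper bound of 23% at a utility gain of 0.02, and is smaller throughout at 0.04. It is a change that should be made, not a flaw that invalidates the evaluation.

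**What to change.** In SAP section 5.2.2.1 b):

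1. Delete the condition that ends the baseline-adjustment sentence.
2. State that the QALY difference in the ICER is the group coefficient from a linear regression of QALY on group, baseline utility and recruitment site, whatever the observed imbalance. Site is included because the SAP's other models adjust for it.
3. State that each of the 10,000 bootstrap samples draws a patient's cost, QALY and baseline utility (with site) together and refits this regression. The plane, the acceptability curve and both limbs of the decision rule then use the adjusted difference.
4. State that this is done within the planned multiple imputation, and in which order imputation and resampling are run.
5. Report the unadjusted ICER and bootstrap as a sensitivity analysis.

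The cost is a few sentences before database lock. No new data are needed, because EQ-5D-5L is collected at baseline. The one practical consequence is that refitting a regression in every sample is better done in Stata, already the main software, than in the Excel bootstrap now named.
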